2 INTRODUCTION

Prostate cancer is the second most frequently diagnosed cancer in men and was estimated to be responsible for over 300,000 deaths worldwide in 2018 (Bray et al. 2018). For patients who require systemic therapy, the mainstay of treatment is hormonal therapy but patients often develop resistance to this therapy (castrate resistant prostate cancer). Treatment for both metastatic and non-metastatic prostate cancer is rapidly evolving. Since the development of a docetaxel regimen for the treatment of metastatic castration-resistant prostate cancer (mCRPC) in 2004 (Tannock et al. 2014), the outcomes of this condition have improved dramatically. However, many of the treatments for prostate cancer, including docetaxel and cabazitaxel for mCRPC, may not be suitable for all patients and some patients are refractory to these treatments, thus there remains a need for additional therapies for this disease.

Current standard of care (SOC) therapies for mCRPC include enzalutamide, and abiraterone plus prednisone. Enzalutamide, a targeted androgen-receptor inhibitor that blocks binding of androgen to the androgen receptor, translocation to the nucleus, and DNA binding (Tran et al. 2009), was approved for the first-line treatment of patients with mCRPC and metastatic castration-sensitive prostate cancer (mCSPC). Abiraterone, a selective inhibitor of 17 α -hydroxylase/C17,20-lyase (CYP17) was also approved in combination with prednisone for the treatment of mCRPC in the first-line setting (Ryan et al. 2013a, Ryan et al. 2013b) and for metastatic high-risk castration-sensitive prostate cancer.

2.1 Study rationale

Although there are now standard of care (SOC) treatments for mCRPC, better treatments are needed for patients after the SOC options have been exhausted.

AZD4635 is being developed as monotherapy and in combination with other agents to augment the anti-tumor immune response. Ongoing studies D8730C00001 and D6070C00004 include the combination of AZD4635 with durvalumab (anti-PDL1 monoclonal antibody) as well as in combination with oleclumab (CD73 mAb), respectively. On study D8730C00001 in the Phase 1A dose escalation portion, 12 patients with metastatic CRPC were dosed with AZD4635, and PSA responses were seen in 4 patients (2 in monotherapy and 2 in combination therapy). Three RECIST responses were seen among these same patients with 1 CR and 2 PRs, all of which persisted for >6 months. Data for the ongoing Phase 1b portion of the study so far support the development of AZD4635 in combination in prostate cancer. Therefore, this open-label multi-center, modular Phase II study in patients with prostate cancer consists of a number of treatment cohorts, allowing evaluation of the efficacy, safety and tolerability of the study drug in multiple treatment arms.

Study rationale for each module is provided in the modular-specific appendix.

2.2 Background

T-cell-mediated immune responses to treatment with immune checkpoint inhibitors have been shown to induce durable responses in several cancers (Larkin et al. 2015, Robert et al. 2015, Brahmer et al. 2015, McDermott et al. 2015, Le et al. 2015, Antonia et al. 2017). However, immune suppression in the tumor microenvironment (TME) can lead to immune evasion, decrease effectiveness of T cells, and impact primary resistance or acquired resistance to immunotherapy. Extracellular adenosine signaling through adenosine 2a receptor ($A_{2A}R$) is one such mediator of immune suppression which leads to decreases in antigen presentation and T cell activation, as well as an increase in suppressive cells. Modulation of the TME with drugs that decrease adenosine or inhibit the $A_{2A}R$ may reverse these effects and enable the host to mount an effective anti-tumor immune response, even in tumor types that are not typically responsive to immune checkpoint inhibitors.

AZD4635 is a potent, highly selective inhibitor of $A_{2A}R$. In preclinical mechanistic, efficacy and pharmacodynamic (PDx) studies, AZD4635 demonstrates activity consistent with enhancement of antitumor immunity. CCI

AZD4635 appears to have increased efficacy in combination with anti-programmed death ligand 1 in prostate cancer due to increased immune activation compared to single agent AZD4635. As of October 4, 2018, in the ongoing study D8730C00001, prostate-specific antigen (PSA) responses were seen in 4 of 10 patients with advanced prostate cancer (2 patients in AZD4635 monotherapy [Phase 1a], and 2 patients receiving AZD4635 in combination with durvalumab [Phase 1a]). In Phase 1a, 8 patients had disease measurable by Response Evaluation Criteria in Solid Tumors version 1.1 (RECIST v1.1) and were observed to have 2 partial responses (1 in a monotherapy cohort, 1 in AZD4635 + durvalumab combination cohorts) and 1 complete response (in an AZD4635 + durvalumab combination cohort). All of these responses persisted for >6 months (11-16 months). Data from this ongoing study appear to suggest a higher response rate in prostate cancer following combination therapy with AZD4635 + durvalumab over AZD4635 monotherapy. Although the combination of anti-CD73 (oleclumab) with AZD4635 has not been studied specifically in

prostate cancer, there is an ongoing study of oleclumab with AZD4635 in refractory epidermal growth factor receptor (EGFR)-mutant non-small cell lung cancer (NSCLC) post-tyrosine kinase inhibitor (TKI) progression. This combination provides inhibition of the adenosine axis by both reduction of adenosine production plus A_{2A}R blockade and is hypothesized to increase the response seen with either single agent alone by further diminishing the adenosine mediated immunosuppression. This hypothesis is also applicable to patients with prostate cancer.

A detailed description of the chemistry, pharmacology, efficacy, and safety of AZD4635 is provided in the Investigator's Brochure (IB).

2.3 Benefit/risk assessment

AZD4635 is a novel A_{2A}R antagonist agent that acts against cancer by blocking adenosine-mediated A_{2A}R signaling in tumor infiltrating cells. AZD4635 blockade is hypothesized to modulate the TME so that an active anti-tumor immune response will be more effective. Therefore, AZD4635 may have the potential to provide benefit in terms of increased efficacy in patients with a variety of advanced solid malignancies and for patients who are refractory to SOC treatments.

As of December 2019, approximately 300 patients with advanced cancer had been treated with AZD4635 alone or in combination with another cancer drug. Between 30 August 2016 and 20 June 2019 (date of data cut-off) in the ongoing study D8730C00001, 94 mCRPC patients were treated with AZD4635 (125 mg BID, 75 mg QD, or 100 mg QD oral nanosuspension Q3W monotherapy [n=49]) or in combination (75 or 100 mg QD) with durvalumab 1.5g IV Q4W (n=45).

As of December 17, 2018, 17 healthy volunteers had received AZD4635 nanosuspension or AZD4635 capsule formulation in study D8730C00002. As of October 05, 2018 in study D6070C00004, 8 patients had received AZD4635 at 2 dose levels in combination with oleclumab.

Based on the available safety data, there are currently no identified risks for AZD4635 when it is used as monotherapy or given in combination with durvalumab or oleclumab. In study D8730C00001, 2 serious adverse events (SAEs) were reported for AZD4635 (at various dose levels) in combination with durvalumab which were considered related to study treatment by the investigators: diabetes mellitus type 1 (Grade 4) and hypertension (Grade 3). In Study D6070C00004, 1 SAE of pulmonary embolism (Grade 3) was considered related to the combination of AZD4635 and oleclumab by the Investigator. Although, thrombosis is considered to be an important potential risk for oleclumab based on known mechanism of action, it is not considered to be a risk for AZD4635.

The most common treatment-emergent AEs (TEAEs) seen in patients treated with AZD4635 as monotherapy or in combination across all studies were mainly nausea, vomiting and fatigue. These AEs were mostly Grade 1 or 2 and were clinically manageable. One patient in study D8730C00001, in the Phase 1a dose-escalation cohort of the combination (75 mg AZD4635 + 1500 mg durvalumab), experienced Grade 2 dose-limiting toxicities (DLTs) of nausea and fatigue which required dose reduction of AZD4635 to 50 mg.

In study D8730C00001, 70 patients were evaluable for tumor response (monotherapy=33, combination=37). RECIST v1.1 responses were confirmed in 8 participants: (monotherapy=ORR 6.1% [2 PRs]) and (combination=16.2% [2CRs, 4PRs]). The median PFS for the monotherapy cohort was 13.6 weeks (95% confidence interval [CI], 7.1-15.3) and 14.9 weeks (95% CI, 13.3-29.3) for the combination cohort. PSA response (defined as $\geq 50\%$ decrease from baseline) was observed in monotherapy=6.4% (3/47 patients; 95% CI, 1.3-17.5%) and combination=20% (9/45 participants; 95% CI, 9.6-34.6%).

More detailed information about the known and expected benefits and risks and reasonably expected AEs of each study drug may be found in their drug-specific IBs and the relevant modules. Appendix A in Modules 1 and 2 describes risk considerations for COVID-19.

3 OBJECTIVES AND ENDPOINTS

Table 3	Study objectives	
	Primary Objective:	Endpoint/Variable:
	To evaluate efficacy of each combination therapy on objective response rate (ORR) for patients with measurable disease	Proportion of patients with measurable disease at baseline who have a confirmed ORR per Response Evaluation Criteria in Solid Tumours (RECIST 1.1)
	To evaluate efficacy of each combination therapy on PSA response rate	PSA confirmed response is defined as the proportion of participants with a reduction in the PSA level of $\geq 50\%$ from baseline to the lowest post-baseline PSA results, measured twice, at least 3 weeks apart by the Prostate Cancer Working Group 3 criteria (PCWG3)
	Secondary Objectives:	Endpoint/Variable:
	To evaluate the efficacy of each combination therapy on the proportion of patients alive and progression free at 6 months	Summaries of the Kaplan-Meier curve for radiological progression-free survival including the proportion of patients alive and radiological progression free at 6 months using RECIST 1.1 (soft tissue lesions) and PCWG3 (bone lesions)
	To evaluate efficacy of each combination therapy on duration of response (DoR)	Duration of Response (DoR) is defined as the time from the date of first documented response until date of documented progression or death in the absence of disease progression
	To evaluate efficacy of each combination therapy on overall survival (OS).	Overall survival is length of time from date of first dose until the date of death due to any cause.

Table 3	Study objectives	
	To evaluate the pharmacokinetics (PK) of AZD4635 and its metabolites and other combination agent(s).	Steady state trough
	To evaluate the immunogenicity of mAB study drug(s) in combination with AZD4635.	Patients with the presence or absence of anti-drug antibody (ADA)
	Safety Objective:	Endpoint/Variable:
	To assess the safety and tolerability of each treatment regimen.	AEs/SAEs Physical exam and vital signs Collection of clinical chemistry/hematology parameters
	Exploratory Objectives	Endpoint/Variable:
	CCI [REDACTED]	CCI [REDACTED]
	CCI [REDACTED]	CCI [REDACTED]
	CCI [REDACTED]	CCI [REDACTED]
	CCI [REDACTED]	CCI [REDACTED]
	CCI [REDACTED]	CCI [REDACTED]
	CCI [REDACTED]	CCI [REDACTED]
	CCI [REDACTED]	CCI [REDACTED]
	CCI [REDACTED]	CCI [REDACTED]
	CCI [REDACTED]	CCI [REDACTED]

Table 3	Study objectives
CCI	CCI

4 STUDY DESIGN

4.1 Overall design

This is an open-label Phase II modular study in patients with prostate cancer to assess safety, efficacy, and tolerability of AZD4635 in combination with other therapeutic agents in different treatment modules. Patients will be randomized for inclusion in the initial 3 modules of AZD4635 plus durvalumab, AZD4635 plus oleclumab, and AZD4635 plus durvalumab plus oleclumab. The decision was made by the Sponsor not to open Module 3 to recruitment after a comprehensive strategy review of the AZD4635 program and not due to new dose-limiting toxicities or concerning safety signals observed with AZD4635.. Patients will be dosed with the capsule formulation of AZD4635.

[figure not shown]
For an overview of the study design see [Figure 1](#), Section 1.2. For details on treatments given during the study, see Section 6.1 Treatments Administered.

For details on what is included in the efficacy and safety endpoints, see Section 3 Objectives and Endpoints.

4.1.1 Modular protocol structure

This study is modular in design and has the potential to include new study drugs in the future via addition of further modules. Information relating to the overall study, including study objectives, rationale, core inclusion and exclusion criteria, safety assessments, and AE reporting can be found in the core protocol. Toxicity management guidelines for AZD4635 are found in Section 8.4.5.

Figure 2 Modular study design^a

^a The decision was made by the Sponsor not to open Module 3 to recruitment after a comprehensive strategy review of the AZD4635 program and not due to new dose-limiting toxicities or concerning safety signals observed with AZD4635.

Study drug-specific information including doses and justifications, toxicity management, dose modifications and concomitant medications for AZD4635 can be found in the core protocol. Study drug-specific information including doses and justifications, toxicity management, dose modifications and concomitant medications for additional study agents can be found in the relevant module.

4.1.1.1 List of modules

The following modules for the study are included with this protocol. The structure of the protocol allows for further modules to be added to the core study via protocol amendment as required.

- Module 1: AZD4635 in combination with durvalumab (Appendix K)
- Module 2: AZD4635 in combination with oleclumab (Appendix L)
- Module 3: AZD4635 in combination with durvalumab and oleclumab (Appendix M)

As stated above, the modules contain study drug-specific information. Specific rationales for these cohorts are provided in the modules.

4.1.2 Clinical screening procedures

Each potential patient will provide informed consent ≤ 28 days prior to the initiation of treatment and before starting any study specific procedures.

Following patient consent, data obtained prior to consent may be used for screening provided the assessments fall within the protocol-specified period prior to the first dose of study drug.

The following screening procedures, which are common to each of the modules, should be performed (please also refer to [Table 2](#)):

- Demographic data and other characteristics will be recorded and will include date of birth or age, gender, and race and/or ethnicity per local regulations.
- A standard medical, medication and surgical history, including prior cancer treatments, response, and duration of prior therapy, will be obtained.
- The following clinical assessments will be required:
 - Physical examination and ECOG performance status evaluation
 - Vital signs + weight and height
 - ECG
 - ECHO/MUGA scan
 - Blood samples collection including testosterone and PSA
 - Urine sample collection
 - Tumor assessments: CT/MRI/PET and Bone scans per RECIST v.1.1 and PCWG3
- All patients will be required to provide an archival tumor block (if available) or a new fresh tumor biopsy if an archival sample is not available (this biopsy sample is not to replace the fresh paired biopsy collection described below).
- A fresh biopsy will be required within 30 days of screening, prior to the first dose of AZD4635, and at week 2 of AZD4635 study treatment, prior to the administration of Cycle 1 Day 1 combinational agent, for all patients for each module until there are sufficient paired samples for the analysis as determined by the Sponsor. In the case that the second sample is not taken, the patient will remain in the study, and there will be no penalty or loss of benefit to the patient, and they will not be excluded from other aspects of the study. The requirement for biopsies must be made clear to each patient at the time of initial approach by the Investigator.
- At screening, consenting patients are assessed to ensure that they meet the core and module-specific eligibility criteria for one or more modules.
- All eligible patients will then be assigned into a module via IWRS system. Randomization will occur when patients meet eligibility criteria for 2 or more modules that are currently recruiting. **If patients only meet the criteria for 1 currently recruiting module, they will be allocated to that module without randomization taking place.**

- All patients, after being assigned into a module, will need to consent for a module specific ICF prior to the 1st dose on study.

Samples for laboratory tests for the assessment of safety will be sent to a local laboratory and assessed locally. All other samples such as those for the assessment of molecular aberrations **CCI** will be assessed centrally. The tumor sample(s) taken as part of the screening procedures will be sent to a central laboratory(ies) for analysis of molecular alterations using tests verified and validated in line with local regulations e.g., Clinical Laboratory Improvement Amendments/College of American Pathologists (CLIA/CAP) for US laboratories, Good Clinical Practice (GCP), and local accreditation for other territories.

4.1.3 COVID-19 testing (if applicable)

During the study, tests for active coronavirus disease of 2019 (COVID-19) infection may be conducted, if required, and in accordance with local guidance.

If a patient is symptomatic for active COVID-19 infection during a site visit, they may be prescribed a COVID-19 test. Dosing may continue while results are awaited, per the Investigator's discretion and local guidelines, and the Medical Monitor/Study Physician should be consulted. If a patient tests positive for COVID-19, the study drugs may be temporarily interrupted and later resumed, per the Investigator's discretion and local guidelines, and this should be discussed with the Medical Monitor/Study Physician. Where applicable, home, or remote visits may be conducted for study assessments and study drug administration (refer to Appendix A in Modules 1 and 2).

4.2 Scientific rationale for study design

Although there are now SOC treatments for prostate cancer, better treatments are needed for patients after the SOC options have been exhausted. AZD4635 is being developed as monotherapy and as an immuno-oncology agent in combination with durvalumab (MEDI4736, PD-L1 monoclonal antibody [mAb]) and in combination with oleclumab (MEDI9447, CD73 mAb), exploiting complementary immune-related mechanisms to broaden and deepen clinical responses in prostate cancer.

AZD4635 had been studied clinically in 3 other investigational trials prior to initiation of this protocol:

- D8730C00001 (NCT02740985): This first-time-in-human (FTIH) study of AZD4635 is a Phase 1 study that dosed AZD4635 at the maximum tolerated dose (MTD) of 100 mg orally (PO) daily (QD) both as monotherapy and in combination with durvalumab in patients with advanced solid tumors.
- D8730C00002 (NCT02740985): A bioavailability study in healthy volunteers was undertaken in order to facilitate a change in formulation and compare the performance of a capsule formulation to the existing nano-suspension to assess the 2 formulation variants.

- D6070C00004 (NCT03381274): AZD4635 is also being studied at 75 and 50 mg PO QD in combination with oleclumab (MEDI9447) 1500 mg intravenously (IV) every 2 weeks (Q2W) in patients with refractory EGFRm lung cancer. Patients developed significant nausea and vomiting at the starting dose of AZD4635 75 mg QD + oleclumab 1500 mg. However, dose reduction to 50 mg AZD4635 nanosuspension daily in combination with oleclumab 1500 mg IV is still under evaluation.

Please see the AZD4635 IB for more information.

4.3 Justification for AZD4635 dose

CCI [Redacted]

[Redacted]

[Redacted]

[Redacted]

Information on dose justification for other study drugs is provided in the respective modules.

4.4 End of study definition

The end of study is defined as the last scheduled visit or contact of the last patient undergoing the study. There will be a primary analysis data cut-off (DCO) for the study (Modules 1 and 2) at approximately 6 months after the last patient starts investigational product (IP) or 90 days after the final patient discontinues IP if this is earlier. The clinical study database will be closed to new data after the DCO for the primary analysis.

The study may be terminated at individual centers if the study procedures are not being performed according to Good Clinical Practice (GCP) or if the site is unable to recruit sufficient numbers of patients into the study.

The AstraZeneca Study Team may also terminate the entire study or individual modules prematurely if concerns for safety arise within this study or in any other study with any agent used in any of the study treatments.

Any patients still receiving IP at the time of the primary study data cut-off can either choose to discontinue from the study or keep receiving IP while deriving clinical benefit as per investigator discretion, following discussion with and approval from the AstraZeneca Study Team. See section 6.8 of this protocol for more information on treatment after the end of this study.

See Appendix A 6 for a description of where protocol information and study results will be made publicly available.

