8.1.1 Tumor assessments with RECIST v1.1

RECIST version 1.1 guidelines for measurable and non-measurable target lesions (TLs) and non-target lesions (NLTs) and the objective tumor response criteria are presented in [Appendix G](#).

Baseline tumor assessments should encompass all areas of known predilection for metastases in the disease under evaluation and should additionally investigate areas that may be involved based on signs and symptoms of individual patients. Baseline assessments should be

performed no more than 28 days before the start of study treatment, and ideally should be performed as close as possible to the start of study treatment. The methods of assessment used at baseline should be used at each subsequent follow-up assessment.

The first follow-up assessment should be initially at 6 weeks (± 1 week) following the start of AZD4635 dosing and subsequent assessments will be performed every 2 cycles (every 8 weeks ± 1 week) thereafter. Any other sites at which new disease is suspected should also be appropriately imaged. If an unscheduled assessment is performed and the patient has not progressed, every attempt should be made to perform subsequent assessments at the scheduled visits.

Categorization of objective tumor response assessment will be based on the RECIST Version 1.1 guidelines for response of soft tissue lesions: CR (complete response), PR (partial response), SD (stable disease), and PD (progression of disease). For patients who only have non-measurable TLs at baseline, categorization of objective tumor response assessment will be based on the RECIST Version 1.1 guidelines for response for NTLs: CR, PD, and Non CR/Non PD.

If the Investigator is in doubt as to whether progression has occurred, particularly with response to NTLs or the appearance of a new lesion, it is advisable to continue treatment and reassess the patient's status at the next scheduled assessment or sooner if clinically indicated.

To achieve "unequivocal progression" on the basis of non-target disease, there must be an overall level of substantial worsening in non-target disease such that, even in presence of SD or PR in target disease, the overall tumor burden has increased sufficiently to merit discontinuation of therapy. A modest "increase" in the size of one or more NTLs is usually not sufficient to qualify for unequivocal PD status.

Calculation or derivation of tumor response variables

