8.3.13 Safety data to be collected following the primary DCO of the study

For patients continuing to receive treatment after primary DCO and database closure, it is recommended that the patients continue the scheduled site visits and Investigators monitor the patient's safety laboratory results prior to and periodically during treatment in order to manage AEs in accordance with the Dose Modification and Toxicity Management Guidelines (see

Section 8.4.5). All data after the primary DCO and database closure will be recorded in the patient notes but, with the exception of SAEs, will not otherwise be reported for the purposes of this study.

All SAEs that occur in patients still receiving treatment (or within the 90 days following the last dose of treatment) after the primary DCO and database closure must be reported as detailed in Section 8.4.1.

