2 or more new metastatic bone lesions are observed compared to the 6-week assessment. The confirmatory scan, performed at least 6 weeks later and preferably at the next scheduled visit for a bone scan, must show the persistence of or an increase in the number of metastatic bone lesions compared to the prior scan for progression to be documented.

The date of progression is the date of the scan that first documents the second lesion.

Evaluation of bone progression status

Table 15 provides the definitions for the visit bone progression status for bone lesions.

Table 15 Bone progression status

Non Progressive Disease (Non-PD)	No evidence of progression, or appearance of one new bone lesion, or non-fulfillment of the progression criteria including new lesions without confirmation of progression.
Progressive Disease (PD)	Bone lesions fulfilling the requirements for at least 2 new lesions and confirmation of progression.
Not Evaluable (NE)	Only relevant if a follow-up bone scan is not performed

OVERALL RADIOLOGICAL VISIT ASSESSMENT

Table 16 provides the definitions how the visit responses for soft tissue (according to RECIST1.1 criteria) and bone progression status (according to PCWG3 criteria) are combined to give an overall radiological objective visit response.

Table 16 Overall radiological visit response

Overall visit soft tissue response (RECIST 1.1)	Bone progression status (PCWG3)	Bone lesions at visit Present/Absent	Overall radiological visit response
CR	Non-PD	Absent	CR
CR	Non-PD	Present	PR
CR	NE	-	PR
PR	Non-PD or NE	Any	PR
SD	Non-PD or NE	Any	SD
NED	Non-PD or NE	Any	Non-PD
NE	Non-PD or NE	Any	NE

Table 16 Overall radiological visit response

Overall visit soft tissue response (RECIST 1.1)	Bone progression status (PCWG3)	Bone lesions at visit Present/Absent	Overall radiological visit response
PD	Any	Any	PD
Any	PD	Any	PD

CR = complete response, PR = partial response, SD = stable disease, PD = progressive disease, NE = not evaluable, NED = No Evidence of Disease (only relevant when there is no TL and NTL from baseline).

CONFIRMATION OF RESPONSE

In the D8731C00001 study, imaging for confirmation of response (CR or PR) should be performed at the next scheduled RECIST and PCWG3 assessment, i.e., 8 weeks (and must not be less than 4 weeks later) following the date the criteria for response were first met.

Table 17 Best overall response when confirmation of CR and PR required.

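### The primary cut-off at about 26 weeks falls before the Week-30 scan that the last-dosed patients need to confirm bone progression or a response first seen at Week 22

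*Protocol*

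**What the plan says.** Section 4.4 sets one primary DCO for both open modules. Its timing is "approximately 6 months after the last patient starts investigational product (IP) or 90 days after the final patient discontinues IP if this is earlier". It adds: "The clinical study database will be closed to new data after the DCO for the primary analysis". Section 8.3.13 repeats the closure: "All data after the primary DCO and database closure will be recorded in the patient notes but, with the exception of SAEs", are not reported for the study.

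The scan calendar is in Section 8.1.1 and Appendix G. "The first follow-up assessment should be initially at 6 weeks" (±1 week), counted from the first AZD4635 dose, and later scans follow every 8 weeks (±1 week).

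The confirmation rules are in Appendix G:
- Response: "imaging for confirmation of response (CR or PR) should be performed at the next scheduled RECIST and PCWG3 assessment, i.e., 8 weeks", with a minimum of 4 weeks. Section 8.1.1 counts only confirmed responses in ORR.
- Bone progression after the first post-baseline scan: the confirming scan is "performed at least 6 weeks later and preferably at the next scheduled visit for a bone scan". Once confirmed, progression is dated to the scan that first showed the second new lesion. Until then Table 15 classes the patient as Non-PD, which covers "non-fulfillment of the progression criteria including new lesions without confirmation of progression".

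Section 9.4.4 censors patients without progression at their last evaluable RECIST assessment or bone scan. The proportion alive and free of radiological progression at 6 months is a secondary endpoint (Section 3).

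**The concern.** The DCO is tied to a calendar interval and not to an assessment. It lands between the Week-22 and Week-30 scans of the last-dosed patients. A finding first seen at Week 22 in these patients is still awaiting confirmation when the database closes, and nothing in the protocol lets the confirming scan in afterwards.

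The bias has a known direction. Real bone progressions drop out of 6-month rPFS as events, which pushes the estimate up. Real late responses drop out of ORR, which pushes it down. Each module has only about 30 patients, about 20 of them with measurable disease, and the stated aim is to choose treatments to take forward, so a single patient is visible in the result.

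**Working it through.** **Plan's own figures.** The Synopsis gives exact Clopper-Pearson 95% intervals, with limits B⁻¹(0.025; x, n−x+1) and B⁻¹(0.975; x+1, n−x).
- 9/30 gives 14.7% to 49.4%.
- 5/20 gives 8.7% to 49.1%.

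Both match. The protocol states no figure for the timing of the cut-off.

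**Calendar.** DCO = 365.25 / 2 / 7 = 26.1 weeks after the last patient's first dose, taking the start of IP as the first AZD4635 dose. Scans fall at 6 + 8k weeks: 6, 14, 22, 30 (±1).

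**Confirmation of a finding first seen at about Week 22, in the last patient:**

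| First seen | Earliest bone confirmation (+6) | Earliest response confirmation (+4) | Planned scan (window) |
|---|---|---|---|
| Week 21 | 27 | 25 | 30 (29–31) |
| Week 22 | 28 | 26 | 30 (29–31) |
| Week 23 | 29 | 27 | 30 (29–31) |

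- Planned scan: 30 − 26.1 = 3.9 weeks after the DCO (2.9 to 4.9 with the window).
- Bone: even the earliest permitted scan is 27 − 26.1 = 0.9 or 28 − 26.1 = 1.9 weeks too late.
- Response: an unscheduled scan at Week 25 or 26 could just precede the DCO; the planned one cannot.

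**Patients exposed.** A patient dosed more than 3.9 weeks (2.9 to 4.9) before the last one reaches Week 30 by the DCO, so only those dosed later are exposed. Two modules of about 30 make 60 patients. The length of accrual is not stated, so uniform accrual over 12 to 20 months is assumed. Exposed = 60 / accrual weeks × 3.9:

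| Accrual (assumed) | Exposed, both modules | Per module | Measurable, per module (× 20/30) |
|---|---|---|---|
| 12 months (52 weeks) | 4.5 | 2.3 | 1.5 |
| 18 months (78 weeks) | 3.0 | 1.5 | 1.0 |
| 20 months (87 weeks) | 2.7 | 1.3 | 0.9 |

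Across the visit window, the total runs from 60/87 × 2.9 = 2.0 to 60/52 × 4.9 = 5.7.

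**Effect on ORR.** Assume that 25% respond (the plan's benchmark) and that 10% to 50% of responses first appear at Week 22 (no source in the protocol). Expected loss per module:
- Low end: 0.9 × 0.25 × 0.10 = 0.02 responders, or 0.02/20 = 0.1 points.
- High end: 1.5 × 0.25 × 0.50 = 0.19 responders, or 0.19/20 = 0.9 points.

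If one whole responder is lost, 5/20 (25%; 8.7% to 49.1%) becomes 4/20 (20%; 5.7% to 43.7%).

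**Effect on 6-month rPFS.** One bone event at Week 22 that is censored instead moves the estimate by about 1/30 = 3.3 points if there is no earlier censoring.

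**The case against.** Several objections have force.

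- A reader might infer that every patient with a Week-22 finding is misclassified. The documents do not support that. Anyone dosed more than about 4 weeks before the last patient reaches Week 30 in time, and findings first seen at Week 6 or 14 can be confirmed by Week 22. Among exposed patients, only a finding that the later scan would have confirmed is wrongly classed.
- For response, Week 30 is the planned scan and not the only valid one. The minimum is 4 weeks, unscheduled assessments are foreseen, and the DCO is only approximate. The ORR part is therefore borderline. However, Appendix G asks for the common schedule to be kept to avoid bias from unequal scan frequency, so off-schedule confirmation is not a planned remedy.
- Any fixed cut-off leaves some responses pending. At Week 31, a response first seen at Week 30 still awaits Week 38. This stands for ORR. It does not reach the bone part, where the event would be dated before the 6-month landmark being estimated.
- Table 15 might suggest that unconfirmed bone progression is counted as progression-free at 6 months. Under Section 9.4.4 it is censored at about Week 22. The bias comes from a lost event, not from a false success.
- The analysis is descriptive, with wide intervals, and PSA response, confirmed after 3 weeks on samples taken each cycle, does not depend on the scan schedule. Both points limit the importance.
- Section 9 leaves missing-data procedures to the SAP. An SAP can say how pending findings are treated, but it cannot recover scans that Section 4.4 keeps out of the database.

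One might also read the 90-day alternative as making this problem worse. It comes earlier than 6 months only if the final patient stops IP by about 26.1 − 12.9 = 13.2 weeks after the last start. The last patient is then off the 8-weekly schedule (Section 8.2.8.2), so the Week-22/Week-30 sequence does not apply to him. That clause is a separate and less likely matter, and no part of this point.

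**Conclusion.** The point holds, and it is minor. For patients dosed within about 4 weeks of the last one (3 to 5 with windows), bone progression first seen at Week 22 cannot be confirmed before a 26-week DCO. The event is lost through censoring, which biases 6-month rPFS slightly upward. A Week-22 response in the same patients misses its planned confirmation and counts against ORR, unless an off-schedule scan happens to fall in time.

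The likely effect is 0 or 1 patient per module. Expected ORR loss is 0.1 to 0.9 points; the 5-point drop is the result of losing one whole responder and not the expected effect. These sizes rest on uniform accrual over 12 to 20 months, two-thirds of patients having measurable disease, and the assumed response timing. The calendar conflict itself rests only on the protocol's own dates, for patients who stay on the 8-weekly schedule.

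**What to change.** In Section 4.4, do one of two things:

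1. Set the primary DCO at the close of the last patient's Week-30 assessment window, that is, Week 31 after his first AZD4635 dose.
2. Keep the 6-month DCO, but hold the database open until already scheduled scans that confirm a response or bone progression first seen by Week 22 have been entered, and state that they are used in the analysis. Sections 6.8 and 8.3.13, which close the database at the DCO, would need the same exception.

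The cost is about 31 − 26.1 = 4.9 weeks' delay and a sentence or two of text. No scans are added, because Week 30 is already on the schedule. The main gain is for 6-month rPFS, since responses first seen at Week 30 would still be pending. A patient who stops treatment soon after Week 22 moves to three-monthly scans, with the next due at about 22 + 13 = Week 35, and would still be missed by a Week-31 cut-off.
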